7.4 Biological Sample Submissions

1. Submission of pathology samples at baseline for diagnostic review is mandatory in order for the patient to be considered evaluable. See Section [10](#) (Pathology Review) and [Appendix II](#) (Pathology Submission Guidelines).
2. Pathology samples for banking should be submitted as outlined in Section [10](#) per patient consent.
3. Blood samples for banking should be submitted as outlined in Section [11](#) per patient consent.

Rev. 9/14

**NOTE:** It is required that biological sample submissions be logged into the ECOG-ACRIN Sample Tracking System (STS) (see Section [10.4](#)) for purposes of monitoring compliance.

**NOTE:** An informed consent must be signed prior to the submission of any samples, including mandatory diagnostic reviews and banking for research in accordance with the patient consent. Samples for banking should be submitted only from patients who have given written consent for the use of their samples for these purposes.

**NOTE:** Institutions outside of the United States and Canada must confer with the receiving laboratory and the ECOG-ACRIN Operations Office - Boston regarding logistics for submission of fresh samples.

Rev. 2/12,  
8/12, 9/14

Biological Materials	Baseline 	After 3 weeks (Arms A/D, and C/F) / 4 weeks (Arms B/E) of Initiating Treatment 	After 12 weeks of Initiating Treatment 	48 weeks 	Progression/Relapse 
MANDATORY for Central Diagnostic Review					
Pathology Samples 	X 				X 
From patients who answer "YES" to "I agree to provide additional blood for research."					
Peripheral Blood (ten 10cc green top heparin tubes) 	X	X	X	X	X 
Peripheral Blood (three 10cc red top tubes) 	X	X	X	X	X 
PAXgene RNA Tube (1) 	X	X	X		
Peripheral Blood, (one 10cc yellow ACD top tube) 	X				

1. Prior to start of treatment.
2. ± 2 weeks.
3. If relapse occurs before the 48 week time point, no additional blood samples are required after the relapse blood sample is sent.
4. Kits are being provided for the collection and shipment of the blood samples. Please refer to Section [11.1.2.1](#) for instructions.
5. **Please completely fill all blood tubes as full as possible.**

Rev. 2/12,  
8/12

- 
- Rev. 3/15 6. Submit to ECOG-ACRIN Central Biorepository and Pathology Facility.
7. Submit to ECOG-ACRIN Immunologic Monitoring and Cellular Products Laboratory.
8. Submit from patients who have consented to have tissue submitted for research.
9. Mandatory submission for central review.
10. [Deleted in Addendum #5]
11. [Deleted in Addendum #5]
- Rev. 8/12, 9/14 12. On the day of the scheduled administration of the second dose of ipilimumab (day 22 +/- 3 days) and **before administering the second dose** of ipilimumab on Arms A, C, D, and F (up to one week prior to the scheduled administration of the second dose is acceptable if not possible on the same day). On the day of initiation of maintenance subcutaneous IFN (day 29 +/- 3days) on Arm B or E (up to one week prior to initiation of maintenance subcutaneous IFN is acceptable if not possible on the same day). If the study treatment was delayed or discontinued for that day due to adverse events the blood specimen should still be collected.

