5.2.2 ARMS B and E: Patients receiving Interferon Alfa - 2b

Rev. 2/13

5.2.2.1 Patients must receive their first injection of IFN Alfa - 2b within 7 working days of randomization.

5.2.2.2 Use actual weight when calculating body surface area.

5.2.2.3 **Induction Phase**

Interferon Alfa - 2b, 20 MU/m^2/d (rounded to the nearest 1.0 million unit) administered **IV** x 5 consecutive days out of 7 (e.g., M-F) every week x 4 weeks.

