**Please complete the following information and include this form in the shipment.**

ECOG Patient Sequence Number: \_\_\_\_\_ ECOG Patient Initials: \_\_\_\_\_  
Last First

Clinical Site: \_\_\_\_\_ Site Contact: \_\_\_\_\_

Telephone Number: \_\_\_\_\_ Fax Number: \_\_\_\_\_

Federal Express® Air Bill No.: \_\_\_\_\_ Date of Shipment: \_\_\_\_\_

Specimen  
Collection Date \_\_\_\_/\_\_\_\_/\_\_\_\_  
mm dd yy

Specimen  
Collection Time: \_\_\_\_:\_\_\_\_  
(24 hour clock)

Time Points (check one):

- Baseline Three (3) red top tubes, Ten (10) green top tubes, One (1) PAXgene RNA tube and One (1) yellow top tube
- Rev. 8/12, 9/14  3 weeks (Arms A/D, C/F)  
4 weeks (Arm B, E) Three (3) red top tubes, Ten (10) green top tubes, one (1) PAXgene RNA tube
- 12 weeks Three (3) red top tubes, Ten (10) green top tubes, One (1) PAXgene RNA tube
- 48 weeks Three (3) red top tubes and Ten (10) green top tubes
- Rev. 8/12 [Deleted in Addendum #5]
- Relapse Three (3) red top tubes and Ten (10) green top tubes

Shipping checklist: (kits will be shipped / delivered to you from UPCI IMCPL upon request)

\_\_\_\_\_ Label vials with patient initials/sequence number, and date and time of draw.

Rev. 2/12

\_\_\_\_\_ [Deleted in Addendum #4]

\_\_\_\_\_ Seal, wrap, and place specimen tubes in specimen shipper kit

Rev. 2/12

\_\_\_\_\_ STS Shipping Manifest Form. Make a copy for your records and place the original form inside the specimen shipper kit.

Rev. 2/12

\_\_\_\_\_ [Deleted in Addendum #4]

To be completed by IML Staff:	IML Study Number
IML Accession Number:	Specimen Type received (if different from above):
Specimen Acceptability:	Comment:

This message is intended only for the use of the individual or entity to which it is addressed and may contain information that is privileged, confidential, and exempt from disclosure under applicable law. If the reader of this message is not the intended recipient or the employee or agent responsible for delivering the message to the intended recipient, you are hereby notified that any dissemination, distribution, or copying of this communications is strictly prohibited. If you have received this communication in error, please notify us immediately by telephone and return the original facsimile to us at the above address via the U.S. Postal Service. Thank you.

---

**A Phase III Randomized Study of Adjuvant Ipilimumab Anti-CTLA4 Therapy Versus High Dose Interferon a-2b for Resected High risk Melanoma**

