#### **XIX.2 Objectives**

1. Primary Objective: Generating prognostic biomarker signature for patients treated with Ipilimumab and high dose IFN $\alpha$  (HDI).
  - a. Aim 1: Testing of specific circulating biomarkers of therapeutically predictive value generated by significant preliminary data
    - i Cellular populations: (1) absolute lymphocyte count; (2) T regulatory (CD4+CD25hi+Foxp3+, CD4+CD25hi+CD39+) and MDSC (monocyte gate HLA-DR+ low/CD14+, monocyte gate Lin1-/HLA-DR-/CD33+/CD11b+, lymphoid gate Lin1-/HLA-DR-/CD33+/CD11b+); (3) IFN $\gamma$ +CD4+ and IFN $\gamma$ +CD8+ antigen specific T cells (gp-100, MART-1, NY-ESO-1 peptides); (4) CD4+ and CD8+ ICOS-hi T cells; (5) IFN $\gamma$ +CD8+CXCR3+VLA4+ T cells
    - ii Serum proteins: CRP, LDH, S100, MIA, YKL40, IL1 $\alpha$ , IL1 $\beta$ , IL2, IL2R $\alpha$ , IL6, IL8, IL10, IL17, IL12p40, TNF $\alpha$ , IFN $\alpha$ , MIP1 $\alpha$ , MIP1 $\beta$ , TNF-RII, TGF- $\alpha$ , TIMP-1, CXCL10 (IP10), CXCL11, CXCL9, VEGF
  - b. Aim 2: Testing of specific biomarkers within the tumor microenvironment (TME) of therapeutically predictive value generated by significant preliminary data
    - i Expression levels of immune related-genes (RNA microarray): CCL2, CCL3, CCL4, CCL5, CD8A, CXCL10, CXCL11, CXCL9, IDO, PRF1, GZMB, HLA-DMA, HLA-DOA, CD79B, IGH, IGKC, IGLC1, HLA-DQA1, IGHM, CD79A, IGHD, CD3G, CD3D, HLA-DPA1, LAT, VAV1, INPP5D, IL2RB, IGHG1, CIITA, IL21R, STAT1

- ii Tumor infiltrating lymphocytes and immunosuppressive markers (immunohistochemistry): CD3, CD4, CD8, FOXP3, PD-L1, IDO, CD45RO

Using known clinical covariates and the markers identified in Aims 1 and 2, we will use the entire data set to develop and validate models capable of identifying which patients belong to different prognostic groups.

2. Secondary Objectives:

- a. Testing the therapeutic predictive value in relation to ipilimumab of the prognostic biomarker signature identified in the primary objective.

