**XIX.3 Choice of Trial**

These correlatives will be utilizing banked biospecimens (pre-treatment and 3-4 weeks post initiation of treatment) in subjects previously consenting to the future use of their banked biospecimens for research purposes. E1609 trial that is testing adjuvant ipilimumab (at high dose and standard dose) versus IFN $\alpha$  in patients with operable stage IIIB/C and M1a/b melanoma who are at high risk for recurrence and death. The large sample size (N ~ 1600) and diverse banked biorepository for E1609 make it an ideal platform through which to evaluate these interrelated markers for their prognostic and immunotherapeutic predictive value with regard to ipilimumab in reference to IFN $\alpha$ , as assessed individually and in combination based on the common systems biology. E1609 will allow the development of a therapeutic predictive model that links circulating markers of the pro-inflammatory response and immunosuppression with markers in the tumor microenvironment. This trial also allows the evaluation of potentially toxicity-predictive biomarkers, the most devastating of which has been autoimmune colitis.

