As expected, because the markers were selected to correlate with outcome, models built from these selected markers also demonstrated prognostic ability in the whole dataset; **Figure 7**. When using the four-marker PH model to predict 5-year OS, we achieved an area under the curve (AUC) 72% (cross validated). High baseline TNF-RII was also significantly associated with worse RFS. The RFS with high (above median) TNF-RII was significantly lower than low TNF-RII ( $p=0.01$ ). Therefore, the biomarker signature consisting of **TNFR-II, TGF- $\alpha$ , TIMP-1** and **CRP** could potentially be used as prognostic markers in patients with high-risk melanoma. These preliminary data warrant further investigation.

**Early on-treatment (one month) pro-inflammatory cytokines predict 1-Year RFS with IFN $\alpha$  but not observation in E1697 trial (Tarhini et al, SMR 2013).** E1697 was a phase III trial that tested observation (Arm A) vs. adjuvant IFN- $\alpha$ 2b for one month (Arm B) in patients (pts) with resected intermediate risk stage IIA-B and IIIA melanoma. We evaluated the levels of candidate serum biomarkers for their therapeutic predictive or prognostic value in Arm B versus Arm A in 268 pts with banked biospecimens. Aushon Multiplex Platform was used for serum cytokine tests at baseline and one month. Cox PH modeling and Wald tests were used to test the association of each marker and RFS. Similar leave-one-out cross validation strategy described above was used to avoid over fitting of the data. In the multi-marker modeling analysis in Arm B, one month IL2R $\alpha$ , IL-12p40 and IFN levels significantly predicted one year RFS with LOOCV AUC=83%. The risk score (linear combination of the 3 markers) separated RFS curves of low and high risk groups well (note that the risk score is calculated using the whole data, hence over fitted.); **Figure 8**. This model did not hold for Arm A, indicating a marker-treatment (IFN) interaction in Arm B, that is consistent with our previously published predictive role of the proinflammatory cytokine profile. Therefore, early on-treatment (one month) proinflammatory serum markers (**IL2R $\alpha$ , IL-12p40, IFN**) significantly predict RFS in pts treated with adjuvant IFN- $\alpha$ 2b and warrant further study.

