### **2.b. Circulating Serum Proteins**

Most serum proteins will be analyzed by the multiplex Luminex assay, and analyzed on a BioRad reader. Concentrations are automatically determined based on kit standard curves from the software. Additional controls include R&D Systems Multiplex QC controls which are mixed cytokines with expected yield values. Large projects use a single lot of kits whenever possible. Analytes requiring non-standard dilutions (like CRP) are run singly. Analytes not compatible with multiplexing are run singly in ELISA format kits. Results are presented as the pg/ml values reported and results above or below the limits of detection are reported as such. Given the broad range of detection for the Luminex platform, values below the LLD are generally considered negative, and values above the ULD are either considered statistically as equal to the ULD, or, if a reasonable fraction of samples are over the ULD, those samples are diluted further and re-run.

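### Appendix XIX treats on-treatment serum IFN-alpha as a candidate marker on HDI, where it can reflect the injected interferon alfa-2b, and the analysis plan has no rule for this

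*Combined protocol and SAP*

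**What the plan says.** Aim 1 in XIX.2 lists 25 serum proteins, opening with "ii Serum proteins: CRP, LDH, S100, MIA, YKL40" and including "IL12p40, TNF $\alpha$ , IFN $\alpha$ , MIP1 $\alpha". XIX.3 says the correlative work uses "banked biospecimens (pre-treatment and 3-4 weeks post initiation of treatment", and XIX.8 includes patients from all arms. The requisition form in Appendix IX confirms that serum is drawn at the on-treatment visit on HDI: "4 weeks (Arm B, E) Three (3) red top tubes". On the assay, XIX.6 item 2.b says "Most serum proteins will be analyzed by the multiplex Luminex assay, and analyzed on a BioRad reader"; it deals with detection limits but not with administered interferon.

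On Arms B and E, Section 5.2.2 gives interferon alfa-2b IV at 20 MU/m2/d "x 5 consecutive days out of 7 (e.g., M-F) every week x 4 weeks", followed by subcutaneous maintenance. Footnote 12 in Section 7.4 places the HDI draw on the day maintenance begins (day 29, plus or minus 3 days) and adds that a draw "up to one week prior to initiation of maintenance subcutaneous IFN is acceptable if not possible on the same day". The same footnote requires the ipilimumab draw to precede the second dose; it has no matching words for HDI. It also asks for the sample when treatment was delayed or stopped for adverse events.

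XIX.9 enters each marker at each time point into a Cox model for RFS with treatment and clinical covariates, and builds a separate prognostic model for each arm. For predictive markers it dichotomises the marker and tests a marker-by-treatment interaction across HDI and ipilimumab.

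**The concern.** On the ipilimumab arms an IFN-alpha value at week 3 is a host measurement. On HDI the same analyte is what the patient is being given, so the week-4 value can be host production, injected drug, or a mixture that depends on when the tube was filled relative to the last dose and on whether doses were held or reduced.

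If such a value enters the HDI prognostic model, an association with RFS could reflect dose received or tolerance of treatment and be reported as host biology. In an interaction test, one cut-point would be applied to arms of which only one receives the analyte. XIX.1 hypothesises a signature from baseline and/or early on-treatment values that is then predictive for ipilimumab, so on-treatment values are within scope for both uses.

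**Working it through.** No power, alpha or sample-size figure is involved. The check is a calendar count plus a reading of the analysis sections.

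**Inputs.** IV induction on 5 days of 7 for 4 weeks (Section 5.2.2). Draw on the day maintenance starts, or up to 7 days before (footnote 12). No collection on Fridays, same-day shipping, Monday to Thursday only (Section 11.2).

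**IV days.** With day 1 a Monday, IV days are 7w + d for w = 0 to 3 and d = 1 to 5: days 1-5, 8-12, 15-19 and 22-26. The last is day 26. Maintenance would start on 4 × 7 + 1 = 29, which agrees with footnote 12.

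**Draw window for a day-29 start: days 22 to 29.**

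| Day | IV dose that day | Days since previous IV dose, if drawn before any dose that day |
|---|---|---|
| 22 (Mon) | yes | 22 − 19 = 3 |
| 23 (Tue) | yes | 23 − 22 = 1 |
| 24 (Wed) | yes | 24 − 23 = 1 |
| 25 (Thu) | yes | 25 − 24 = 1 |
| 26 to 28 (Fri to Sun) | day 26 only | ruled out by collection and shipping rules |
| 29 (Mon) | no | 29 − 26 = 3 |

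With no pre-dose rule, a draw on days 22-25 may also follow that day's infusion by minutes or hours, and a day-29 draw after the first subcutaneous dose is not excluded. If maintenance starts on day 32, a draw that day is 32 − 26 = 6 days after the last IV dose. Held doses lengthen the gap, and Section 5.5.2 allows induction doses of 13.3 or 6.6 MU/m2 after modification.

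**What the analysis does with this.** The covariate lists in XIX.9 contain no time since dose, dose received or exclusion for IFN-alpha. The treatment term in the single-marker model absorbs the average difference between arms, not variation within HDI. The HDI-only model has no treatment term to absorb anything.

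**The documents' own evidence.** XIX.4 reports that in E1694 serum IFN-alpha and IP-10 rose after HDI. It also reports a one-month score of IL2R-alpha, IL-12p40 and IFN that predicted 1-year RFS in the interferon arm of E1697 (cross-validated AUC 83%) but not under observation, and recommends further study of these "early on-treatment (one month) proinflammatory serum markers". A marker that tracks administered drug could give the same pattern.

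**The case against.** The strongest reply is that inclusion is deliberate: E1697 nominates one-month IFN, and a prognostic marker need not come from the host. That explains why IFN-alpha is on the list. It does not resolve the ambiguity, because the E1697 score has it too and the plan interprets such markers as immune response.

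The reach is limited, and this stands. IFN-alpha is one of 25 proteins, affected at one time point in one arm. XIX.9 names the ipilimumab models as the main goal. The predictive section does not say that on-treatment values will be used, so bias in every HDI-versus-ipilimumab contrast is not established. Random timing noise would tend to weaken an association, and final models face a held-out set.

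Four stronger readings are tempting, and the documents do not support them:

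- A reader might count dosing days in the window and infer that a large share of samples was drawn on drug. The early draw is only a fallback, windows for different start dates cannot be pooled, and a day-22 draw before infusion has the same 3-day gap as day 29.
- A reader might put a fold-difference on drug level. No half-life is given. Assuming anything from 2 to 24 hours, the fraction left at 72 hours is 2^(−72/2) = 1.5 × 10^(−11) to 2^(−72/24) = 12.5%, too wide to size the problem. At the short end, a day-29 pre-dose sample holds almost no drug whether or not the last doses were given, so low values from held doses would arise mainly in fallback or post-dose draws.
- A reader might infer that IL-6, CXCL9, CXCL11 and lymphocyte count mainly record draw time. XIX.4 shows a rise after HDI for IP-10 and IFN-alpha; it gives no hours-to-days kinetics for the others.
- A reader might conclude that footnote 12 needs amending. Section 9.3 reports adult accrual complete in August 2014, with adolescent accrual to stay open only until 2016, so few if any week-4 draws would remain.

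**Conclusion.** The point holds as an analysis gap in the correlative study. IFN-alpha is a listed marker, week-4 HDI serum is assayed, the patient is then receiving interferon alfa-2b, and no rule in XIX.8-9 distinguishes drug from host production. The permitted time since dose runs from just after an infusion to 3 days nominally and 6 days for a day-32 start, longer with held doses. The day counts assume a Monday start and the Monday-to-Friday example schedule. The number of affected samples and the size of any distortion cannot be stated from the documents. The case is firm for IFN-alpha, supported for IP-10, and only a reason for a sensitivity check for the other week-4 markers. It is worth correcting because the correction is cheap. The RFS and OS co-primary analyses are untouched.

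**What to change.** In XIX.8-9, before the validation set is opened:

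- State that in HDI patients on-treatment IFN-alpha is a drug-exposure measure, not a candidate host marker. Keep it out of the HDI prognostic model and the cross-arm dichotomised marker-by-treatment tests. Baseline IFN-alpha remains a candidate.
- For the other week-4 HDI markers, add a sensitivity analysis that either excludes samples drawn on an IV dosing day or adjusts for days since the last recorded dose. Collection date and time are on the tube label (Section 11.1.2) and the requisition form (Appendix IX); combine these with dosing dates. Work in days, since the documents do not show that clock times of IV infusions are recorded.

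The cost is appendix wording and a record linkage. The candidate nominated by E1697 is lost as an on-treatment marker on HDI, and some HDI week-4 samples drop out of the sensitivity analysis.

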## 8. Drug Formulation and Procurement

This information has been prepared by the ECOG-ACRIN Pharmacy and Nursing Committees.

### Availability

Drug Ordering: Bristol-Myers-Squibb is supplying ipilimumab, through the Division of Cancer Treatment and Diagnosis, NCI, for this protocol. Maintenance of NCI drug accountability records is required. Ipilimumab (NSC 732442) (IND) may be requested by the Principal Investigator (or their authorized designees) at each participating institution. Pharmaceutical Management Branch (PMB) policy requires that drug be shipped directly to the institution where the patient is to be treated. PMB does not permit the transfer of agents between institutions (unless prior approval from PMB is obtained – see general information). Completed Clinical Drug Requests (NIH-986) should be submitted to the PMB by [contact] or mailed to the Pharmaceutical Management Branch, CTEP, DCTDC, NCI, [name], Bethesda, M.D. 20892. The NCI Clinical Drug Request form is available on the NCI home page (<http://ctep.info.nih.gov>) or by calling the PMB at [contact].

Rev. 2/14

Rev. 2/14

### NCI Supplied Agent(s) – General Information

**NOTE:** Under no circumstances can commercially supplied ipilimumab be used or substituted for the NCI-supplied ipilimumab.

**Questions about drug orders, transfers, returns, or accountability should be addressed to the PMB by calling [contact] Monday through Friday between 8:30 AM and 4:30 PM Eastern Time.**

Rev. 2/14

**Drug Returns:** All unused drug supplies must be returned to the PMB. When it is necessary to return study drug (e.g., sealed vials remaining when a patient permanently discontinues protocol treatment, expired vials recalled by the PMB), investigators must return the study drug to the PMB using the NCI Return Agent Form available on the NCI home page (<http://ctep.cancer.gov>) or by calling the PMB at [contact].

Rev. 2/14

**Drug Accountability:** The investigator, or a responsible party designated by the investigator, must maintain a careful record of the receipt, disposition, and return of all drugs received from the PMB using the NCI Investigational Agent Accountability Record available on the NCI home page (<http://ctep.cancer.gov>) or by calling the PMB at [contact].

Rev. 2/14

#### 8.1 Ipilimumab

In this study, the investigational product is ipilimumab.

##### 8.1.1 Drug Name

Ipilimumab (NSC 732442)

##### 8.1.2 Other Names

Anti-CTLA-4 monoclonal antibody, MDX-010 (MDX-CTLA4, Transfectoma-derived)

##### 8.1.3 Classification

Human monoclonal antibody, IgG1 subclass

M.W.: 147, 991 Daltons

Ipilimumab has two manufacturing processes- ongoing trials have been using substances manufactured using Process B. This trial, E1609, uses ipilimumab that is manufactured by Process C. The Process C has been developed using a higher producing sub-clone of the current Master Cell Bank, and modified cell culture and purification steps.

